7.2. Informed Consent Procedures

Before protocol-specified procedures are carried out, consenting professionals will explain full details of the protocol and study procedures as well as the risks involved to participants prior to their inclusion in the study. Participants will also be informed that they are free to withdraw from the study at any time. All participants must sign an IRB/PB-approved consent form indicating their consent to participate. This consent form meets the requirements of the Code of Federal

Version Date: 11/09/2017

Regulations and the Institutional Review Board/Privacy Board of this Center. The consent form will include the following:

- 1. The nature and objectives, potential risks and benefits of the intended study.
- 2. The length of study and the likely follow-up required.
- 3. Alternatives to the proposed study. (This will include available standard and investigational therapies. In addition, patients will be offered an option of supportive care for therapeutic studies.)
- 4. The name of the investigator(s) responsible for the protocol.
- 5. The right of the participant to accept or refuse study interventions/interactions and to withdraw from participation at any time.

Before any protocol-specific procedures can be carried out, the consenting professional will fully explain the aspects of patient privacy concerning research specific information. In addition to signing the IRB Informed Consent, all patients must agree to the Research Authorization component of the informed consent form.

Each participant and consenting professional will sign the consent form. The participant must receive a copy of the signed informed consent form.

8. TREATMENT PLAN

Treatment will be administered on an outpatient basis. Reported adverse events and potential risks for pembrolizumab and epacadostat are described in Section 8. Appropriate dose modifications for pembrolizumab and epacadostat are described in Section 9. No investigational or commercial agents or therapies other than those described below may be administered with the intent to treat the patient's malignancy.

8.1. Pembrolizumab Administration

Pembrolizumab is approved by the US Food and Drug Administration for the treatment of metastatic melanoma, non-small cell lung cancer, head and neck cancer, and unresectable or metastatic, microsatellite instability-high (MSI-H) or mismatch repair deficient (dMMR) solid tumors that have progressed following prior treatment and who have no satisfactory alternative treatment options. Subjects will receive pembrolizumab 200 mg (flat dose) IV every 3 weeks on day 1 of a 21 day cycle.

Study treatment should be administered after all procedures/ assessments have been completed as detailed in the schedule of assessments (Section 12 & 13). All study treatments will be administered on an outpatient basis. Pembrolizumab will be administered as a 30 minute IV infusion. At the end of the infusion, the line should be flushed with a sufficient quantity of normal saline.

Version Date: 11/09/2017

8.1.1. Management of Pembrolizumab Infusion Reactions

Signs and symptoms usually develop during or shortly after drug infusion and generally resolve completely within 24 hours of completion of infusion.

The table below shows treatment guidelines for subjects who experience an infusion reaction associated with administration of pembrolizumab (MK-3475).

Infusion Reaction Treatment Guidelines

NCI CTCAE Grade	Treatment	Premedication at subsequent dosing
Grade 1 Mild reaction; infusion interruption not indicated; intervention not indicated	Increase monitoring of vital signs as medically indicated until the subject is deemed medically stable in the opinion of the investigator.	None
Grade 2 Requires infusion interruption but responds promptly to symptomatic treatment (e.g., antihistamines, NSAIDS, narcotics, IV fluids); prophylactic medications indicated for <=24 hrs	Stop Infusion and monitor symptoms. Additional appropriate medical therapy may include but is not limited to: IV fluids Antihistamines NSAIDS Acetaminophen Narcotics Increase monitoring of vital signs as medically indicated until the subject is deemed medically stable in the opinion of the investigator. If symptoms resolve within one hour of stopping drug infusion, the infusion may be restarted at 50% of the original infusion rate (e.g., from 100 mL/hr to 50 mL/hr). Otherwise dosing will be held until symptoms resolve and the subject should be premedicated for the next scheduled dose. Subjects who develop Grade 2 toxicity despite adequate premedication should be permanently discontinued from further trial treatment administration.	Subject may be premedicated 1.5h (± 30 minutes) prior to infusion of pembrolizumab (MK-3475) with: Diphenhydramine 50 mg po (or equivalent dose of antihistamine). Acetaminophen 500-1000 mg po (or equivalent dose of antipyretic).
Grades 3 or 4 Grade 3: Prolonged (i.e., not rapidly responsive to symptomatic medication and/or brief interruption of infusion); recurrence of symptoms following initial improvement; hospitalization indicated for other clinical sequelae (e.g., renal impairment, pulmonary infiltrates) Grade 4: Life-threatening; pressor or ventilatory support indicated	Stop Infusion. Additional appropriate medical therapy may include but is not limited to: IV fluids Antihistamines NSAIDS Acetaminophen Narcotics Oxygen Pressors Corticosteroids Epinephrine Increase monitoring of vital signs as medically indicated until the subject is deemed medically stable in the opinion of the investigator. Hospitalization may be indicated.	No subsequent dosing

Version Date: 11/09/2017

NCI CTCAE Grade	Treatment	Premedication at subsequent dosing
	Subject is permanently discontinued from	
	further trial treatment administration.	
Appropriate resuscitation equipment show administration.	uld be available in the room and a physician read	ily available during the period of drug

8.2. Epacadostat Administration

Epacadostat will be dosed at 100 mg PO BID daily. Doses should be taken twice daily, in the morning and evening, approximately 12 hours apart, without regard to food. If a dose is late but within 4 hours of its scheduled administration time it should be taken; if more than 4 hours have passed, the dose should be omitted and the patient should continue treatment with the next scheduled dose. If vomiting occurs while taking epacadostat, no redosing is allowed before the next rescheduled dose.

For epacadostat, patients will not require any premedications, however supportive medications to control symptoms such as nausea, emesis, diarrhea, and pain will be provided for symptom control (Section 9.2 for management of immune related adverse effects).

Doses will be self-administered, except on Cycle 2 Day 1, when the morning dose will be given at the study site clinic. Subjects will be required to keep a pill diary (Appendix D). Each cycle of treatment will last 21 days.

8.3. General Concomitant Medication and Supportive Care Guidelines

Medications or vaccinations specifically prohibited in the exclusion criteria are not allowed during the ongoing study. If there is a clinical indication for 1 of these or other medications or vaccinations specifically prohibited during the study, discontinuation from study therapy may be required.

8.3.1. Restricted Medications and Measures

- Systemic steroids may be used at doses of prednisone ≤ 10 mg/day, or equivalent.
- Use of coumarin-based anticoagulants (eg, Coumadin) is discouraged. Low-dose Coumadin® (1 mg) is acceptable; however, doses that increase the INR are discouraged and will require dose modification. If an alternative to coumarin-based anticoagulants cannot be used, dose modifications of the Coumadin® may be needed. Based on the observed magnitude of epacadostat/warfarin PK interaction and PK/PD modeling results, for an epacadostat dose of 300 mg BID, the dose of warfarin should be reduced by approximately one-third after initiation of epacadostat administration based on approximately 30% to 40% reduction in S- and R-warfarin oral clearance values. Close

Version Date: 11/09/2017

INR monitoring is recommended for subjects on a stable dose of warfarin who are starting treatment with epacadostat. Based on PK/PD modeling, recommendations for warfarin dose modifications for subjects receiving other epacadostat doses are summarized in Table below based on the INR prior to starting epacadostat.

Warfarin Dose Adjustment Recommendation when Initiating Concurrent Epacadostat Treatment

	Epacadostat Dose			
Stable Baseline INR	≤ 100 mg BID	200 mg BID	300 mg BID	
INR ≤ 2.5	Close INR monitoring	Close INR monitoring	Reduce warfarin by ~33% and monitor INR	
INR > 2.5	Close INR monitoring	Reduce warfarin by 20%-25% and monitor INR	Reduce warfarin by ~33% and monitor INR	

• Use of the anticonvulsant carbamazepine (a UGT1A9 inducer) is discouraged. Because there is a potential interaction that could result in lower epacadostat exposures, an alternative to carbamazepine should be used, if possible.

8.3.2. Prohibited Medications and Measures

Subjects are prohibited from receiving the following therapies during the screening and treatment phase of this study unless otherwise noted below:

- Any investigational medication other than the study drugs.
- Any anticancer medications, including chemotherapy or biologic therapy other than the study medications.
- Any immunological-based treatment for any reason.
 - Note: Inhaled or topical steroids are allowed, and systemic steroids at doses ≤ 10 mg/day prednisone or equivalents are allowed, and immune suppressants are allowed for treatment for immune toxicities.
- Radiation therapy
 - O Note: Radiation therapy to a symptomatic solitary lesion or to the brain may be allowed after consultation with the principal investigator.
- Live Administration of live attenuated vaccines within 30 days before the first dose of study treatment and while participating in the study is prohibited. Examples of live vaccines include, but are not limited to, the following: measles, mumps, rubella, chicken pox, yellow fever, rabies, BCG, and typhoid vaccine. Seasonal influenza vaccines for injection are generally killed virus vaccines and are allowed; however, intranasal influenza vaccines (eg, FluMist®) are live attenuated vaccines and are not allowed.
- Any melatonin supplements.
- Any MAOI or drug associated with significant MAO inhibitory activity agents is prohibited from 21 days before Day 1 through 2 weeks after the final dose of epacadostat has been taken (see Appendix C).

Version Date: 11/09/2017

- Any UGT1A9 inhibitor, including acitretin, amitriptyline, androsterone, cyclosporine, dasatinib, diclofenac, diflunisal, efavirenz, erlotinib, estradiol (17-beta), flutamide, gefitinib, gemfibrozil, glycyrrhetinic acid glycyrrhizin, imatinib, imipramine, ketoconazole, linoleic acid supplements, mefenamic acid, mycophenolic acid, niflumic acid, nilotinib, phenobarbital, phenylbutazone, phenytoin, probenecid propofol*, quinidine, ritonavir, sorafenib, sulfinpyrazone, valproic acid, and verapamil.
 - *Note Propofol, when used for short-term sedation during surgical/biopsy procedures, is allowed after consultation with the principal investigator. The epacadostat dose may be taken on the morning of the procedure, and the evening dose held following the procedure. Epacadostat may be resumed the next day.

Subjects who, in the assessment by the investigator, require the use of any of the aforementioned treatments for clinical management should be removed from the study. Subjects may receive other medications that the investigator deems to be medically necessary.

The exclusion criteria describe other medications that are prohibited during this study. There are no prohibited therapies during the post-treatment follow-up phase.

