8.6. Duration of Treatment

The subject will continue to receive study treatment as long as the subject is receiving benefit from treatment and has not met any criteria for study withdrawal (Section 6.6). If the subject discontinues study treatment, the treatment phase will end and the subject will enter the follow-up phase (Section 12).

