Toxicity Note: Exception to be treated similar to Grade 1 toxicity: - Grade 2 alopecia - Grade 2 fatigue - Grade 3 rash in the absence of desquamation, without mucosal involvement, not requiring systemic steroids, and that resolves to Grade 1	2	Consider holding for persistent symptoms	Toxicity resolves to ≤ Grade 1 or baseline	Restart at same dose for non-immune related AEs *See section 9.2 for management of immune-related AE's that may require dose reductions. If dose reduction is required: Reduce dose to 50 mg PO BID. If 50 mg PO BID is not tolerated, then epacadostat should be discontinued.	Restart at same dose *See section 9.2 for management of immune- related AE's that may require dose reductions.	Toxicity does not resolve within 6 weeks of last infusion. Permanent discontinuation should be considered for any severe or life-threatening event.
within 14 days * See section 9.2 for immune-related AE's	3	Yes	Toxicity resolves to ≤ Grade 1 or baseline	Reduce dose to 50 mg PO BID. If 50 mg PO BID is not tolerated, then epacadostat should be discontinued.	Restart at same dose	Toxicity does not resolve within 6 weeks of last infusion. Permanent discontinuation should be considered for any severe of life-threatening event.
	4	Yes	Discontinue treatment	Treatment with epacadostat may not be restarted	Treatment with pembrolizumab may not be restarted	Toxicity does not resolve within 6 weeks of last infusion. Permanent discontinuation

Columbia University Medical Center Herbert Irving Comprehensive Cancer Center Version Date: 11/09/2017

			should be considered for any severe of life-threatening event.

Note: Subjects who experience a recurrence of the same severe or life-threatening AE at the same grade or greater treatment should be discontinued from study treatment.

Version Date: 11/09/2017

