9.3. Procedures for Subjects Exhibiting Serotonin Syndrome

There is a theoretical chance that epacadostat could cause an increase in serotonin levels in the brain that might trigger serotonin syndrome (SS) when administered in combination with other serotonergic agents. This syndrome has been most closely associated with use of MAOIs, Demerol®, linezolid, or methylene blue; all of these agents are prohibited during the study. Serotonin reuptake inhibitors (SSRIs) and serotonin/norepinephrine reuptake inhibitors (SNRIs) are permitted in the study. The following procedures will be implemented if subjects exhibit the signs/symptoms of SS, including tremor, hyperreflexia, spontaneous, ocular, or inducible clonus, together with agitation, fever, diaphoresis, or muscle rigidity:

- Immediately interrupt epacadostat administration. *Administration of pembrolizumab may continue*.
- Immediately interrupt any SSRI or SNRI administration.
- Provide appropriate medical management of the subject until all signs/symptoms are resolved (eg, IV fluids and/or sympathomimetic amines for hypotension, benzodiazepines for agitation, administration of 5-hydroxytryptamine antagonists such as cyproheptadine).
- If subject chooses to remain in the study, restart treatment with epacadostat after the SSRI or SNRI has been discontinued, no sooner than 5 half-lives have elapsed for the specific SSRI or SNRI in question and after resolution of signs/symptoms of SS. The SSRI or SNRI treatment MAY NOT be restarted.
- If subject chooses to withdraw from the study, or must restart treatment with SSRI or SNRI, the subject should be scheduled for a follow-up visit. Treatment with SSRI or SNRI may be initiated 2 weeks after resolution of signs and symptoms of SS.

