12.4. Follow-up Phase

12.4.1. Safety Follow-up

The safety follow-up phase is the interval between the last dose of study treatment and the scheduled safety follow-up visits, which should occur on days 30 (+/- 7 days) after the EOT visit. Adverse events and SAEs must be reported up until at least 90 days after the last dose of study drug, or until study drug-related toxicities resolve, return to baseline, or are deemed irreversible,

Version Date: 11/09/2017

whichever is longer. If a subject initiates a new anti-cancer therapy within 90 days after the last dose of study treatment, the next scheduled safety follow-up visit must occur before the first dose the new therapy. Once new anti-cancer therapy has been initiated, the subject will move into the survival follow-up phase.

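### The closing sentence of Section 8.3.2 lifts every drug restriction in follow-up, although the same section bans MAO inhibitors for 2 weeks after the last epacadostat dose

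*Combined protocol and SAP*

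**What the plan says.** Three parts of Section 8.3.2 matter here.

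- The lead-in sets the scope of the list: "Subjects are prohibited from receiving the following therapies during the screening and treatment phase of this study unless otherwise noted below".
- The MAOI bullet sets its own dates. These drugs, listed in Appendix C, are "prohibited from 21 days before Day 1 through 2 weeks after the final dose of epacadostat has been taken".
- The final paragraph first says that subjects who "require the use of any of the aforementioned treatments for clinical management should be removed from the study", and then closes with "There are no prohibited therapies during the post-treatment follow-up phase".

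Two other sections say when follow-up begins. Under Section 8.6, when a subject discontinues study treatment, "the treatment phase will end and the subject will enter the follow-up phase". Under Section 12.4.1, "The safety follow-up phase is the interval between the last dose of study treatment and the scheduled safety follow-up visits".

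Section 9.3 names MAOIs, Demerol, linezolid and methylene blue as the agents most closely linked to serotonin syndrome, and adds that "all of these agents are prohibited during the study". SSRIs and SNRIs are allowed on study.

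**The concern.** The MAOI bullet and the closing sentence give opposite answers about the same days. A pharmacist or treating physician asking what may be given once study treatment has stopped would naturally turn to the sentence that names that phase. Read literally, it permits linezolid, meperidine or methylene blue the day after the last epacadostat dose.

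The patient most exposed is one taken off study because an Appendix C drug is needed. The same paragraph removes that patient and then appears to clear the drug at once. Because SSRIs and SNRIs are permitted, such a patient could also be taking another serotonergic agent. The 2-week tail is a precaution against serotonin syndrome, and the closing sentence removes it on paper.

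**Working it through.** The plan states no figure on this point, so the check is a timeline comparison.

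**Inputs**

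- End of the ban: day 14 after the final epacadostat dose (8.3.2).
- Start of follow-up: the day of discontinuation (8.6) or the last dose of study treatment (12.4.1).
- Visits: an end-of-treatment (EOT) visit with a +7-day window, and a safety visit 30 ± 7 days after EOT (Section 13, Table 12).
- Drugs covered: Appendix C lists 15 MAOI entries and 3 drugs with MAO-inhibiting activity, so 15 + 3 = 18.

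**Overlap.** Let d be the number of days from the final epacadostat dose to the start of follow-up. Then overlap = max(0, 14 − d).

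| d | Days of the ban inside follow-up |
|---|---|
| 0 | 14 − 0 = 14 |
| 7 | 14 − 7 = 7 |
| 14 or more | 0 |

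**Which d applies**

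- *Both drugs stopped for good on the same day.* d = 0 under both sections, so the overlap is 14 days.
- *Both drugs held for toxicity, then discontinued.* Section 9.1 calls for both to be interrupted together, and Table 1 allows up to 6 weeks from the last infusion for recovery. Counted from the last dose (12.4.1), d is still 0 if epacadostat was the last drug taken. Counted from discontinuation (8.6), d is the length of the hold, and a hold of 14 days or more leaves no overlap.
- *Epacadostat stopped alone.* Table 1 provides for this: "If 50 mg PO BID is not tolerated, then epacadostat should be discontinued". If pembrolizumab continues for 14 days or more, the whole tail lies in the treatment phase and the overlap is nil.

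**Would scheduled visits settle it?** Table 12 places concomitant medication review at EOT and at the 30-day visit, and the serotonin-syndrome check at EOT only. Assume that EOT falls 0 to 7 days after stopping. The 30-day visit then falls between day 0 + 23 = 23 and day 7 + 37 = 44. That is 23 − 14 = 9 to 44 − 14 = 30 days after the ban has ended. It can come earlier: Section 12.4.1 moves the safety visit ahead of new anticancer therapy, and Section 6.6.1 asks early discontinuers to return within 30 days. These reviews can detect use of an Appendix C drug. They do not say which sentence governs.

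**Other restrictions that can outlast treatment.** Section 8.3.2 bars live attenuated vaccines for as long as the subject participates in the study. Section 9.3 delays an SSRI or SNRI until 2 weeks after serotonin syndrome has resolved in a subject who withdraws or must restart such a drug. The closing sentence makes no allowance for either.

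**The case against.** The strongest reply is that the section can be read so that it agrees with itself. The lead-in confines the list to screening and treatment unless a bullet says otherwise, and the MAOI bullet does say otherwise. The closing sentence is then only the general counterpart of the lead-in, and a specific, dated rule naming the drug class prevails. Section 9.3 points the same way. This stands as evidence of intent: it shows which sentence to correct. It does not remove the conflict, because the lead-in's proviso qualifies its own list. The closing sentence comes later, concerns follow-up specifically, and has no exception or cross-reference.

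The reply on weight also largely stands. Exclusion criterion 13 calls the risk theoretical and unreported to date, and a site that withholds these drugs for 14 days breaches neither sentence.

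A reader might infer that every patient's full 14 days fall in follow-up. The documents do not support that: the overlap is nil when pembrolizumab continues for 14 days or more, and under Section 8.6 also when both drugs are held that long before discontinuation. A reader might also infer that the MAOI tail is the only restriction the closing sentence contradicts. The vaccine and SSRI/SNRI rules show that it is not.

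**Conclusion.** The contradiction is real. Its size is between 0 and 14 days of the ban per patient, and it reaches the full 14 whenever follow-up starts at the final epacadostat dose. The range rests on Sections 8.6 and 12.4.1 for the start of follow-up, since the closing sentence does not define the phase it refers to. The visit-day figures rest on the stated assumption about EOT timing.

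It would go too far to say that the protocol leaves its intention open or that patients are likely to be harmed. The dated bullet is evidently the rule meant, and the documents give no rate of Appendix C drug use from which to estimate how many patients would be affected. Nor does the error touch the response endpoint, the Simon design or any analysis. It is a minor wording error, worth correcting because sites act on this text and the subject is safety.

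**What to change.** Keep the closing sentence of Section 8.3.2 and add to it: *unless otherwise specified in this protocol; in particular, MAOIs and the other drugs in Appendix C remain prohibited until 2 weeks after the last epacadostat dose.*

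The general proviso is needed as well as the named exception. A sentence listing MAOIs as the sole exception would strengthen the implication that live vaccines and early SSRI or SNRI use are permitted.

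The cost is one clause. A patient who needs an Appendix C drug inside the window must use an alternative or wait. The MAOI bullet already requires that and carries no exception for clinical need. Section 8.3 and the removal sentence in 8.3.2 provide for taking such a patient off treatment or off study, but neither says whether the 2-week tail then still applies. If the sponsor wants a medical-necessity exception for that patient, this amendment is the place to state it.
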